GLP-1	Glucagon-Like Peptide-1
HbA1c	Hemoglobin A1c
HDPE	High Density Polyethylene
HIPAA	Health Insurance Portability and Accountability Act
HOMA-IR	Homeostatic Model Assessment and Insulin Resistance
hs-CRP	High-sensitivity C-Reactive Protein Hip-to-Waist Ratio
HWR	Hip-to-Waist Ratio
HTN	Hypertension
ICF	Informed Consent Form
ITT	Intent-To-Treat
IRB	Institutional Review Board
OPC	Out-Patient Clinic
PI	Principle Investigator
SAP	Statistical Analysis Plan
T1D	Type 1 Diabetes
USP	United States Pharmacopeia
1,5-AG	1,5-Anhydroglucitol

SIGNATURE PAGE

Study Title:	Study to Evaluate the Effects of BKR-017 on Insulin Sensitivity and Triglycerides in Type 1 Diabetes Subjects
Protocol Date and Version:	July 13, 2023Amendment5, Version6
Protocol Number:	CL-301
Investigator:	[name] Mayo Clinic [name]
Institutional Review Board:	Mayo Clinic Institutional Review Board [REDACTED] [name]

We, the undersigned, have carefully read this protocol and agree that it contains all the necessary information required to conduct the trial and that it complies with principles of Declaration of Helsinki.

Investigator:

[name]

Signature

Date (month/dd/year)

CLINICAL PROTOCOL SYNOPSIS					Protocol No.:	CL-301		
Sponsor: Mayo Clinic					Investigator: [name]			
Title of Study: Study to Evaluate the Effects of BKR-017 on Insulin Sensitivity and Triglycerides in Type 1 Diabetes Subjects								
Study Center: Mayo Clinic, Rochester, MN							Country: US	
Objectives: To evaluate effect of colon-targeted butyrate tablets (BKR-017) on insulin sensitivity and triglycerides in type 1 diabetes subjects.								
					Number of Tablets		Dose	
Test Group	Test Product	No. of Subjects	Dose Regimen	Dosing Duration (days)	Each dose (tablets)	Daily (tablets)	Single Dose	Total Daily Dose
1	Active	16	BID	48	3	6	1.5 g	3.0 g
Test Product: BKR-017 is an oral tablet formulation designed to target delivery of butyrate to the colon via a colon-targeting technology. [REDACTED]								
[REDACTED]								
[REDACTED]								
[REDACTED] The tablets will be supplied by BioKier in 150-ml high density polyethylene (HDPE) white bottles.								
Design: This study will test effect of BKR-017 (colon-targeted 500 mg butyrate tablets) as adjuvant therapy in type 1 diabetes (T1D) Subjects on metabolic control in this population. Insulin sensitivity, insulin usage, glucose control (variability), and triglycerides will be measured after 7 weeks of treatment and compared to Day -28.								
Number of Subjects: Assuming a 30% (approximate) early discontinuation rate, 16 Subjects will be consented and enrolled to ensure that 13 Subjects complete the 11-week study (4-week run in and 7 -week treatment period).								
Diagnosis and Main Criteria for Inclusion: Criteria for Subject recruitment will be: 20–80 years of age; type 1 diabetes with C-Peptide (CPR) less than 0.5 ng/mL; HbA1c level of 6.4–8.9%; at week -4. The study design will be a single-arm, open-label study. Subjects will be expected to use the Dexcom G6 Continuous Glucose Monitor (CGM) system and be willing to share their data via the CLARITY app with the study team.								
Duration of Subject Enrollment: Eleven (11) weeks; baseline period 28 days (4 weeks), treatment period: 48 days (7 weeks). Two visits will be required: one screen visit and one visit after 48 days of treatment.								
STUDY PERIOD (See Time and Events Schedule, Section 6)								
Baseline Period (Day -28):								
Visit 1 (Day -28): Following web- and phone-based pre-screening, subjects who remain eligible will be scheduled for a screening visit. Subjects will be asked to arrive for the screening visit (Visit 1) in a fasted state (10-hour fast). Subjects will be consented prior to obtaining any biological samples or performing any study procedures. Subject eligibility will be assessed, demographics, medical history, and concomitant medications will be obtained along with- height, weight, waist and hip circumference to calculate Hip-to-Waist Ratio (HWR), and an abbreviated physical exam will be performed (including signs for edema). Fasting samples will be obtained for glucose and triglycerides. Additional blood samples will be obtained for HbA1c, routine hematology, and routine chemistry assessments. Hypertension (HTN) will be determined from medical history and concomitant medications. Blood pressure will be measured and used, along with HbA1c, to calculate the eGDR (estimated Glucose Disposal Rate). A urine pregnancy test will be obtained for females of childbearing potential.								

CLINICAL PROTOCOL SYNOPSIS	Protocol No.:	CL-301
Sponsor: Mayo Clinic	Investigator:	[name]

After signing consent and meeting all inclusion criteria, subjects will be instructed on, and supplied with a study provided Dexcom G6 sensors , to collect glucose data. Subjects will be instructed to keep their Dexcom CLARITY app active, so that glucose monitoring data can be accessed by the study team throughout the study. Diary cards will be provided for the subject to record insulin doses, changes to concomitant medications and adverse events. Diary cards will be mailed/emailed to the study team every 7 to10 days throughout the study. Subjects using an insulin pump, will be advised to mail/email a copy of their pump settings and insulin doses every 7 to10 days or upload their pump data to a prespecified, linked online account compatible with their pump (i.e. Medtronic CareLink, Tandem T Connect or Glooko), whereby the relevant data can be abstracted by the study team.
 
An eight-week supply of investigational product (BKR-017) will be provided to subjects. Subjects will not start dosing until Day 0.
 
During the entire study, subjects will be asked to maintain their daily routines, including diet and exercise. Females of childbearing potential and able to become pregnant, must agree to use one of the birth control methods listed in the consent form, for the duration of the study.
 
Treatment Period: Day 0 to Day 48:
 
Day 0 will occur approximately 28 days after the screen visit (agreed upon with the subject). The study team will communicate with the subject via a phone call or virtual visit on this day. After ensuring that the CGM data collected is acceptable, subjects will be instructed to commence taking the investigational product (BKR-017) as instructed.
 
Subjects will be instructed to keep their Dexcom CLARITY app active, so that glucose monitoring data can be accessed by the study team. Subjects will continue to fill out diary cards, to record insulin doses, changes to concomitant medications and adverse events. Diary cards will be mailed/emailed to the study team every 7 to 10 days. Subjects using an insulin pump, will be advised to mail/email a copy of their pump settings and insulin doses every 7 to 10 days or upload their pump data to a prespecified, linked online account compatible with their pump (i.e., Medtronic CareLink, Tandem T Connect or Glooko), whereby the relevant data can be abstracted by the study team.
 
Subjects will be contacted by the study team on Days 18 and 28, to assess study compliance, review concomitant meds and adverse events.
 
Final Visit (Day 48):
 
At the final study visit, Visit 2 (Day 48), fasting samples (10-hour fast) will be obtained for glucose and triglycerides. Additional blood samples will be obtained for HbA1c, routine hematology, routine chemistry assessments, CPR, and the exploratory tests 1,5 AG and hs-CRP. Blood pressure, height, weight, waist and hip circumference to calculate HWR, be obtained and an abbreviated physical exam will be performed. A urine
		

CLINICAL PROTOCOL SYNOPSIS		Protocol No.:	CL-301
Sponsor: Mayo Clinic		Investigator: [name]	
pregnancy test will be obtained for females of childbearing potential. The CGM sensor will be removed, and data downloaded.			
Subjects will be required to return the study CGM sensor, all unused test product in the original container along with any diary cards at this visit. The diary card and returned product will be reconciled by the study staff, and medication changes and adverse events recorded on the diary will be reviewed.			
Subjects with the following conditions will be excluded: History of bariatric or intestinal surgery, currently pregnant, nursing, or trying to become pregnant, type 2 diabetes, active gastrointestinal disease (e.g., irritable bowel syndrome, inflammatory bowel disease (e.g., ulcerative colitis, Crohn’s Disease, diverticulitis, gastroparesis, chronic/frequent diarrhea or chronic/frequent constipation), active and clinically significant hepatic, renal, or pancreatic disease, history of congestive heart failure, prior MI or significant cardiovascular disease, hepatic, renal, or pancreatic disease, history of congestive heart failure, prior MI or significant cardiovascular disease, uncontrolled hypertension uncontrolled hyper- or hypothyroid disease, active infection or history of trolled hypertension uncontrolled hyper- or hypothyroid disease, active infection or history of hepatic, renal, or pancreatic disease, history of congestive heart failure, prior MI or significant cardiovascular disease, uncontrolled hypertension uncontrolled hyper- or hypothyroid disease, active infection or history of chronic infection, subjects reporting an anticipated change in exercise or diet, subjects on a high fiber diet, subjects with pitting edema, and subjects who, in the investigator’s judgment, are not suitable for the study for any other reason, or subjects who cannot commit to the requirements of the study.			
Subjects currently taking the following therapies are excluded: GLP-1 receptor agonists (e.g., Byetta®, Bydureon®, Adlyxin®, Victoza®, Saxenda®, Trulicity®, Tanzeum®, Ozempic®), Amylin analogs (e.g., Symlin®), Thiazolidinediones (e.g., Actos®, Avandia®) and any combination of these medications (e.g., Avandamet®, Avandaryl®, Duetact®, Actoplus Met®, PioMet®), Acarbose (Glucobay®), Miglitol (Glyset®). Additionally, subjects taking oral and injectable corticosteroids (e.g., prednisone), oral and injectable antibiotics, opioids and probiotics or other medications that alter gastrointestinal motility, chemotherapy, radiation, cytotoxic therapy, immune suppressants, antiepileptic drugs, colesevelam (Welchol®), and other supplements containing butyrate are also excluded from the study.			
Efficacy and Safety Evaluations			
Primary	Insulin sensitivity, as measured by the estimated glucose disposal rate (eGDR), a validated clinical tool for estimating insulin sensitivity in T1D		
Secondary	The following secondary evaluations will be performed: 1. Glucose variability 2. Triglycerides 3. Insulin usage, as reported on diary card		
Safety	Blood pressure, physical exam, chemistry, hematology and treatment-emergent adverse events		
Exploratory	1,5 AG and hs-CRP		

CLINICAL PROTOCOL SYNOPSIS		Protocol No.:	CL-301
Sponsor: Mayo Clinic		Investigator: [name]	
Statistical Analysis of Primary Endpoint:	Primary and Secondary Efficacy Data: The primary endpoint is the change from baseline (Day 0) to Day 48 in insulin sensitivity as measured by eGDR. The secondary endpoint of glucose variability (as measured from CGM data) is also the change from baseline (Day 0) to Day 24 and Day 48. However, the secondary endpoint of lowering of triglycerides measurements will be calculated from the baseline at Day -28.		
	Safety Data: Assessment of safety will be made using the change from baseline in vital signs, physical exam, chemistry, hematology, and treatment-emergent adverse events. The safety analysis set will include all Subjects that received any amount of study treatment. The safety analysis set will include all Subjects that received any amount of study treatment.		
	Sample Size Estimates: Sample size estimates are based on practical considerations.		
Synopsis Date: July 18, 2022, Amendment 2, Version 3.0			

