4. STUDY POPULATION

4.1 Number of Subjects

Approximately 28 subjects with T1D will be screened to determine eligibility. Sixteen eligible subjects will be enrolled into the study with the expectation that 13 will successfully complete the study.

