11.2 Sample Size

Differences in eGDR (mg/kg/min) between Days -28, and 48 will be assessed by calculating eGDR from HWR (Hip-to-Waist Ratio), blood pressure, and HbA1c, off treatment and on treatment. for each subject. Statistical significance will be assessed by comparing eGDR at each of Day -28 and Day 48 to eGDR at Day -28 (i.e., baseline) with a paired t-test.

This study of 12 subjects is considered large enough to draw some preliminary clinical conclusions.

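### Sixteen enrolled at the stated 30% discontinuation gives about 11 completers, not the 13 promised, and Section 11.2 rests on a third number, 12

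*Combined protocol and SAP*

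**What the plan says.** Three places give numbers of subjects for the study.

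- **Synopsis, Number of Subjects.** The entry reads: "Assuming a 30% (approximate) early discontinuation rate, 16 Subjects will be consented and enrolled to ensure that 13 Subjects complete the 11-week study". The 11 weeks are the 4-week run-in plus the 7-week treatment period, so the rate applies to the whole course from enrolment.
- **Section 4.1.** "Sixteen eligible subjects will be enrolled into the study with the expectation that 13 will successfully complete the study". Here 13 is an expectation, and no discontinuation rate is given. Screening losses are counted separately: "Approximately 28 subjects with T1D will be screened to determine eligibility".
- **Section 11.2, Sample Size.** "This study of 12 subjects is considered large enough to draw some preliminary clinical conclusions". The section does not say whether 12 means enrolled, completing or evaluable.

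On the basis for the size, the synopsis adds: "Sample size estimates are based on practical considerations". No significance level, power, effect size or standard deviation is given anywhere.

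**The concern.** The synopsis supplies a starting number, a loss rate and a result, so the result can be checked, and it does not follow. Section 11.2 then makes the plan's only statement that the study is large enough, and makes it about a number that is neither the enrolment nor the stated completer count.

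The completer count matters because it is in effect the largest number of pairs available to the primary analysis, a paired t-test of eGDR at Day 48 against Day -28. Section 12.2 imputes nothing. Section 7.3.1 calculates eGDR from hip-to-waist ratio, blood pressure and HbA1c, while the termination visit in Section 9.2 lists vital signs, chemistry and hematology but no waist or hip measurement. As written, a subject who stops early has no post-baseline eGDR, and the ITT set does not recover that pair. A reader cannot tell whether 11, 12 or 13 completers would meet the plan.

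**Working it through.** **Inputs.** Enrolled N = 16 (synopsis, Section 4.1); discontinuation d = 0.30, described as approximate (synopsis); completers 13 (synopsis, Section 4.1); study size 12 (Section 11.2).

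**1. Attempt to reproduce the plan's figure.** Enrolment needed for a target number of completers is target/(1 − d).

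- For 13 completers: 13/0.70 = 18.6, so 19. The plan has 16.
- For 12: 12/0.70 = 17.1, so 18.
- For 11: 11/0.70 = 15.7, so 16. This is the only one of the three targets that returns 16.

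The common but incorrect inflation, target × (1 + d), gives 13 × 1.30 = 16.9, so 17, and 12 × 1.30 = 15.6, so 16. The 16 may therefore have come from a target of 12 inflated the wrong way. The documents do not say so, and this is conjecture.

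**2. Forward calculation.** Expected completers = N × (1 − d) = 16 × 0.70 = **11.2**, against 13 stated. The gap is 1.8 subjects, or 1.8/13 = 14% of the target.

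**3. Discontinuation implied by each completer count.**

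- 13 of 16: 1 − 13/16 = 18.75%
- 12 of 16: 1 − 12/16 = 25%
- 11 of 16: 1 − 11/16 = 31.25%

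**4. How likely 13 is.** Take the number completing as Binomial(16, 1 − d). This assumes independent drop-out at a common rate, which the documents do not state.

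| d | Expected completers of 16 | P(13 or more) | Enrolled for 13 expected |
|---|---|---|---|
| 20% | 12.8 | 0.598 | 17 |
| 25% | 12.0 | 0.405 | 18 |
| 30% | 11.2 | 0.246 | 19 |
| 35% | 10.4 | 0.134 | 20 |

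At 30%, P(12 or more) = 0.450. Enrolling 19 would make 13 the expected result but would not guarantee it: P(13 or more of 19) = 0.666. That probability reaches 0.908 with 22 enrolled and 0.945 with 23.

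**5. Effect on precision.** The 95% confidence interval half-width for a mean paired change, in units of the SD of the change, is t(0.975, n − 1)/√n:

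- n = 13: 0.604
- n = 12: 0.635
- n = 11: 0.672

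From 13 to 11 pairs the interval widens by 0.672/0.604 − 1 = 11%.

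**The case against.** The strongest reply concerns consequence. The size is declared to rest on practical grounds, the study is single-arm and open-label, and Section 11.2 claims only preliminary conclusions. No power or precision target is built on 13 or 12, so no stated operating characteristic is wrong, and the interval widens by only 11%. All of that stands and limits the weight of the point. It does not make the figures agree.

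Three narrower replies:

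- **The 12 may be an adequacy threshold.** Section 11.2 asserts 12 and derives nothing from it, so expecting 13 completers would satisfy it. This reading is possible, but it does not help: the plan's own rate gives about 11, below the threshold, with a 45% chance of reaching 12.
- **Run-in losses may not count.** Section 9.1 treats anyone who never receives test product as a screen failure. The synopsis, however, applies its rate to subjects already consented and enrolled and to completion of the full 11 weeks, run-in included.
- **Completers are not an analysis set.** Every efficacy analysis is run on the ITT and per-protocol populations, and the per-protocol dose rule can remove a completer. That is correct, so the half-widths above are illustrative. The dose rule can only lower the number of pairs.

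It is also fair to say that the documents do not show which figure is wrong. Twelve of 16 implies 25% loss, which is closer to the stated rate than 13 of 16 at 18.75%.

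**Conclusion.** The inconsistency is real. Under its own assumption the plan delivers about 11 completers rather than 13, and the 12 in Section 11.2 matches neither the enrolment, nor the stated completers, nor what the stated rate yields. Calling the rate approximate does not close the gap, because 13 is the expected result only if loss falls to about 19%. The expected-value arithmetic needs nothing beyond the plan's figures; the probabilities also need independent drop-out at a common rate. The consequence is modest: no power claim is affected, and the primary comparison would rest on about two fewer pairs than stated. It should still be corrected, because the plan's only adequacy statement should refer to a number the design is expected to produce.

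**What to change.** State one enrolment, one discontinuation rate and the completer number that follows from them, in the same terms in the synopsis, Section 4.1 and Section 11.2. The sponsor knows which input was wrong; the coherent choices are:

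- **Keep 16 and 30%:** about 11 expected completers. This needs no new subjects and no new assumption.
- **Keep 16 and 12:** discontinuation of 25%.
- **Keep 16 and 13:** discontinuation of about 19%, with a reason for the lower rate.
- **Keep 13 and 30%:** enrol 19. This adds three subjects and, at the planned ratio of 28 screened to 16 enrolled, brings screening to about 19 × 28/16 = 33.

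Under any of these, describe the completer number as expected rather than ensured, and replace the 12 in Section 11.2 with that number, saying whether it means completers or subjects with an evaluable eGDR pair. For the first choice, Section 11.2 could read:

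> *Sixteen subjects will be enrolled. With about 30% discontinuation, approximately 11 are expected to complete and contribute to the paired comparison of eGDR. With 11 pairs, the half-width of the 95% confidence interval for the mean change is about 0.67 standard deviations of the change. The size was chosen on practical grounds.*

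The precision sentence is an addition rather than a correction, but it gives the adequacy statement some content (0.60 SD if 13 is retained). Apart from the fourth choice, the cost is wording in three places; the first two choices also lower the stated completer number.

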6.2.2 Termination of Baseline Period, Initiation of Test Period

Day 0, the following will be performed:

1. Subjects will be instructed to administer the first dose of test product prior to their mid-day meal and the second daily dose just prior to bedtime on Day 0.
2. Subjects will be instructed to keep their Dexcom CLARITY app active, so that glucose monitoring data can be accessed by the study team.
3. Subjects will be reminded to mail/email diary cards to the study team every 7 to 10 days. Subjects using an insulin pump, will be advised to mail/email a copy of their pump settings and insulin doses every 7 to 10 days or upload their pump data to a prespecified, linked online account compatible with their pump (i.e. Medtronic CareLink, Tandem T Connect or Glooko), whereby the relevant data can be abstracted by the study team.
4. Subjects will also be instructed not to make any modifications to their diet or exercise routine.
5. Subjects will be scheduled to return to the OPC for Visit 2 and instructed to return all unused tablets in the original container(s) along with any diary cards.

On Day 48 (Visit 2, Final Visit):

1. Subjects will report to the OPC in the morning, before 12:00 noon. If a subject is not able to comply with the Day 0 requirement, a variance of -2 days (or Day 46 or 50) is allowed.
2. Urine pregnancy test will be obtained for females of childbearing potential.
3. Subjects will return all unused tablets in the original container(s) along with any diaries.
4. Blood pressure, height, weight, and waist and hip circumference will be obtained to calculate the WHR. Fasting samples will be obtained for glucose and triglycerides. Additional blood samples will be obtained for HbA1c, routine hematology, routine chemistry assessments CPR, and for exploratory biomarkers hs-CRP and 1,5AG.
5. An abbreviated physical exam will be performed.
6. Study staff will review the subject's diary in order to reconcile tablets returned with any doses missed.

7. Subjects will be questioned about any changes in health status/adverse events and any changes in therapy or medications
8. Study personnel will remove the CGM sensor from the subject's abdomen and download the data to the Dexcom CLARITY data storage location.

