12.6.2 Secondary Efficacy Analysis

Blood glucose variability will be calculated for each subject, for each 24-hour day (midnight to midnight) during which a CGM device recording is available for the entire 24-hour period. Results will be presented graphically for each subject by study day.

Triglyceride changes at Day -28 and Day 48 will be summarized as change from baseline where Day -28 is considered baseline.

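### The stated glucose-variability change cannot be computed at Day 48 for subjects seen on Day 46 to 48, and its Day 0 baseline is a mixed day; fixed multi-day CGM windows would mend both

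*Combined protocol and SAP*

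**What the plan says.** Three places describe the glucose-variability comparison, and they differ.

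- **Synopsis, statistical analysis:** "glucose variability (as measured from CGM data) is also the change from baseline (Day 0) to Day 24 and Day 48".
- **Synopsis, Design:** insulin sensitivity, insulin usage, glucose variability and triglycerides "will be measured after 7 weeks of treatment and compared to Day -28".
- **Section 12.6.2:** variability is calculated per subject for each midnight-to-midnight day "during which a CGM device recording is available for the entire 24-hour period", and is shown as a graph by study day. There is no change score, baseline, window or test.

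Other sections decide which days can supply a value.

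- **Start of dosing:** the synopsis states "Subjects will not start dosing until Day 0". Section 6.2.2 tells subjects to "administer the first dose of test product prior to their mid-day meal and the second daily dose just prior to bedtime on Day 0".
- **End of recording:** for Visit 2, Section 6.2.2 says "Subjects will report to the OPC in the morning, before 12:00 noon" and, as the last listed step, "Study personnel will remove the CGM sensor".
- **Visit window:** Section 6.2 allows two days either side, so Visit 2 may fall on Day 46 to Day 50.
- **Missing data:** Section 12.2 leaves missing values missing.

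**The concern.** The two days named as the ends of the change are poor choices for a measure that needs a whole calendar day. Day 0 includes the first two doses, so it is not a purely untreated day. Day 48 is the scheduled day of sensor removal, so for a subject seen on time it is never a whole day.

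Reduced glucose variability is a named expected benefit in the Introduction and an assessed effect in Section 2. If the definition stays as it is, the end-of-treatment change exists only for subjects who attend late, or someone must choose other days once the data are visible. In an open-label, single-arm study that choice could affect the result.

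**Working it through.** **1. The plan's own figures.** Section 5.4 gives 96 required doses. Two doses a day over Days 0 to 47 is 2 × 48 = 96, which matches. Days 0 to 48 inclusive would give 98. Days 1 to 48 would also give 96, but Section 6.2.2 places two doses on Day 0, so Days 0 to 47 is the reading that fits. Section 7.3.2 gives a reading every 5 minutes and up to 2880 in 10 days: 24 × 60 / 5 = 288 a day, and 288 × 10 = 2880, which also matches.

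**2. Is there a Day 48 value?** The last complete day is the day before the sensor comes off.

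| Visit 2 on | Last complete day | Complete Day 48? |
|---|---|---|
| Day 46 | 45 | No |
| Day 47 | 46 | No |
| Day 48 | 47 | No |
| Day 49 | 48 | Yes |
| Day 50 | 49 | Yes |

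If removal were at noon on Day 48, at most 144 of 288 readings (50%) would exist. The protocol gives no removal time, but removal at any hour that day fails the complete-day rule.

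**3. How mixed is Day 0?** Assume the first dose is taken between 10:00 and 13:00. The pre-dose share of the day is then 10/24 = 42% to 13/24 = 54%, and the post-dose share is 58% to 46%. Suppose half the day is post-dose, a fraction f of the eventual effect is present in those hours, and the day's value averages linearly over its hours. The measured change is then reduced by 0.5 × f: 0% for f = 0, 25% for f = 0.5, 50% for f = 1. The documents give no value for f.

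**4. What data exist?** With visits on nominal days, the complete pre-dose days are Day -27 to Day -1 (27 days) and the complete on-product days are Day 1 to Day 47 (47 days). These are ceilings: a sensor lasts up to 10 days (Section 7.3.2), and changes or gaps may cost some days. Day 24 lies inside continuous recording, so the Day 24 contrast shares only the Day 0 problem.

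**5. What would averaging gain?** Let s be the day-to-day SD within a subject.

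- Difference of two single days: SD = s√2.
- Difference of two 14-day means: SD = s√(2V), where V is the variance of a 14-day mean in units of s².
- Ratio = 1/√V, which does not depend on s.
- Independent days: V = 1/14, ratio = √14 = 3.7.
- First-order autocorrelation of 0.5: V = 1/5.2, ratio = √5.2 = 2.3.

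The window length and the autocorrelation are assumptions. The calculation covers day-to-day noise only and leaves out drift within a subject between the two periods.

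**The case against.** The strongest reply is that Day 0 and Day 48 were never meant as single calendar days. The same synopsis paragraph uses a Day 0 baseline for eGDR, yet the Time and Events Schedule has no blood pressure, waist and hip measurement or HbA1c on Day 0. The label may therefore be shorthand for the baseline period, which Section 6.2.1 runs from Day -28 to Day 0. The synopsis also carries an older version label (Amendment 2, Version 3.0) than the protocol (Amendment 5, Version 6). Section 12.6.2 plans only graphs, where an absent Day 48 is one point among many, and Section 12.1 refers to an SAP for further detail. This is a fair account of how the text may have arisen, and it lowers the severity. But no section supplied defines a CGM window, and the synopsis sentence is the only definition of the change that stands.

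A reader might also infer more than the documents support:

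- **That the sensor comes off before noon.** Only the subject's arrival is timed.
- **That Day 0 is simply an on-product day.** Roughly half of it is pre-dose, and Section 1 describes release in the colon over eight or more hours, so the early effect may be small.
- **That Day -28 is necessarily a part day because study sensors are supplied then.** Inclusion criterion 7 requires current Dexcom use, so some subjects may already be recording.
- **That the run-in record is ignored.** Section 12.6.2 graphs it; it is only the stated change that leaves it out.
- **That the study loses a known amount of power.** No test, alpha, SD or variability metric is given for this endpoint, so any detectable-change figure would rest on assumed values.

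**Conclusion.** The point holds as a fault of definition. Applied literally, the Day 48 change is uncomputable for every subject seen on Day 46 to 48 and computable only for those seen on Day 49 or 50. Its baseline is a mixed day with contamination of unknown size, and the synopsis names two different baselines. The Day 48 conclusion rests on the single-day reading together with the complete-day and no-imputation rules; it needs no assumption about removal time. The 3.7-fold and 2.3-fold noise ratios are illustrations under stated assumptions.

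No data are lost, and the primary endpoint and safety are untouched. This is a SHOULD-FIX, best settled before anyone examines the CGM results.

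**What to change.** In the synopsis and Section 12.6.2, replace the Day 0, Day -28 and Day 48 single-day references for CGM measures with one pre-specified change:

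- **Baseline:** each subject's mean daily variability over a fixed window ending on Day -1, for example Days -14 to -1.
- **On-product value:** the mean over a window of the same length ending on the last complete day before the actual Visit 2, for example Days 34 to 47 for a visit on Day 48, or Days 32 to 45 for a visit on Day 46.
- **Exclusions:** leave out Day 0 and the visit day.
- **Early leavers:** use only days after Day 0, so that run-in days cannot enter the on-product window.
- **Computability:** name the variability metric and state the minimum number of valid days in each window. A subject below the minimum stays missing, as Section 12.2 requires.
- **Mid-course value, if kept:** use a window around Day 24 under the same rules.

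The 14-day length is a choice; what matters is that it is fixed in advance and equal on both sides. The cost is wording and slightly more analysis. No new data, visits or subjects are needed, and the dosing instructions are not affected.
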